9.4 Early study termination by the sponsor

The study can be terminated by Novartis at any time.

Reasons for early termination:

- Unexpected, significant, or unacceptable safety risk to participants enrolled in the study
- Decision based on recommendations from applicable board(s) after review of safety and efficacy data
- Discontinuation of study drug development

In taking the decision to terminate, Novartis will always consider participant welfare and safety. Should early termination be necessary, participants must be seen as soon as possible and treated as a participant who discontinued from study treatment. The investigator may be informed of additional procedures to be followed in order to ensure that adequate consideration is given to the protection of the participant's interests. The investigator or sponsor depending on local regulation will be responsible for informing IRBs/IECs of the early termination of the trial.

10 Safety monitoring, reporting and committees

10.1 Definition of adverse events and reporting requirements

10.1.1 Adverse events

An AE is any untoward medical occurrence (e.g. any unfavorable and unintended sign [including abnormal laboratory findings], symptom or disease) in a clinical investigation participant after providing written informed consent for participation in the study. Therefore, an AE may or may not be temporally or causally associated with the use of a medicinal (investigational) product.

The investigator has the responsibility for managing the safety of individual participants and identifying AEs.

Novartis qualified medical personnel will be readily available to advise on trial related medical questions or problems.

The occurrence of AEs must be sought by non-directive questioning of the participant at each visit during the study. Adverse events also may be detected when they are volunteered by the participant during or between visits or through physical examination findings, laboratory test findings, or other assessments including PROs and diary (refer to [Section 8.5.1](#)).

AEs must be recorded under the signs, symptoms, or diagnosis associated with them, accompanied by the following information (as far as possible) (if the event is serious refer to [Section 10.1.2](#)):

1. The severity grade:
 - mild: usually transient in nature and generally not interfering with normal activities
 - moderate: sufficiently discomforting to interfere with normal activities
 - severe: prevents normal activities
2. The causality the investigator is obligated to assess the relationship between any treatment (study medication or AxMPs) used in the study and each occurrence of each AE. The investigator will use clinical judgment to determine the relationship. A reasonable possibility of a relationship conveys that there are facts, evidence, and/or arguments to suggest a causal relationship, rather than a relationship cannot be ruled out. Alternative causes, such as underlying disease(s), concomitant therapy, and other risk factors, as well as the temporal relationship of the event to study intervention administration, will be considered and investigated. If the event is due to lack of efficacy or progression of underlying illness (i.e. progression of the study indication) the assessment of causality will usually be 'Not suspected.' The rationale for this guidance is that the symptoms of a lack of efficacy or progression of underlying illness are not caused by the trial drug, they happen in spite of its administration and/or both lack of efficacy and progression of underlying disease can only be evaluated meaningfully by an analysis of cohorts, not on a single participant.
3. Its duration (start and end dates or ongoing) and the outcome must be reported.
4. Whether it constitutes a SAE (see [Section 10.1.2](#) for definition of SAE) and which seriousness criteria have been met.
5. Action taken regarding inclisiran/placebo, or rosuvastatin.
All AEs must be treated appropriately. Treatment may include one or more of the following:
 - Dose not changed
 - Dose reduced/increased for rosuvastatin
 - Drug interrupted/permanently discontinued
6. Its outcome can be:
 - not recovered/not resolved;
 - recovered/resolved;
 - recovering/resolving,
 - recovered/resolved with sequelae;
 - fatal;
 - or unknown

Conditions that were already present at the time of informed consent should be recorded in medical history of the participant.

AEs (including lab abnormalities that constitute AEs) should be described using a diagnosis whenever possible, rather than individual underlying signs and symptoms.

Once an AE is detected, it must be followed until its resolution or until it is judged to be permanent (e.g. continuing at the end of the study), and assessment must be made at each visit (or more frequently, if necessary) of any changes in severity, the suspected relationship to the interventions required to treat it, and the outcome.

Information about adverse drug reactions for the investigational drug can be found in the Investigator's Brochure (IB) or local SmPC.

Information about adverse drug reactions for rosuvastatin can be found in the local SmPC.

Abnormal laboratory values or test results constitute AEs only if they fulfill at least one of the following criteria:

- they induce clinical signs or symptoms
- they are considered clinically significant
- they require therapy

Clinically significant abnormal laboratory values or test results must be identified through a review of values outside of normal ranges/clinically notable ranges, significant changes from baseline or the previous visit, or values which are considered to be non-typical in participant with the underlying disease.

Reporting of AEs related to AxMP(s)

All AEs related to any authorized auxiliary medicinal product used in this study must be reported to Novartis.

In assessing causality, the investigators will use the points mentioned in the paragraph above.

If a suspicion that medical occurrence could be related to AxMP cannot be ruled out, the reporting rules for study treatment apply.

10.1.2 Serious adverse events

An SAE is defined as any AE [appearance of (or worsening of any pre-existing)] undesirable sign(s), symptom(s), or medical conditions(s) which meets any one of the following criteria:

- fatal
- life-threatening

Life-threatening in the context of a SAE refers to a reaction in which the participant was at risk of death at the time of the reaction; it does not refer to a reaction that hypothetically might have caused death if it were more severe (please refer to the ICH-E2D Guidelines).

- results in persistent or significant disability/incapacity
- constitutes a congenital anomaly/birth defect

- requires inpatient hospitalization or prolongation of existing hospitalization, unless hospitalization is for:
 - routine treatment or monitoring of the studied indication, not associated with any deterioration in condition (coronary heart disease, cerebrovascular disease or peripheral vascular disease)
 - elective or pre-planned treatment for a pre-existing condition that is unrelated to the indication under study and has not worsened since signing the informed consent
 - social reasons and respite care in the absence of any deterioration in the participant's general condition
 - treatment on an emergency outpatient basis for an event not fulfilling any of the definitions of a SAE given above and not resulting in hospital admission
- is medically significant, e.g. defined as an event that jeopardizes the participant or may require medical or surgical intervention to prevent one of the outcomes listed above

Medical and scientific judgment should be exercised in deciding whether other situations should be considered serious reactions, such as important medical events that might not be immediately life threatening or result in death or hospitalization but might jeopardize the participant or might require intervention to prevent one of the other outcomes listed above. Such events should be considered as “medically significant.” Examples of such events are intensive treatment in an emergency room or at home for allergic bronchospasm, blood dyscrasias, or convulsions that do not result in hospitalization or development of dependency or abuse (please refer to the ICH-E2D Guidelines).

All new malignant neoplasms will be assessed as serious under “medically significant” if other seriousness criteria are not met.

Any suspected transmission via a medicinal product of an infectious agent is also considered a serious adverse reaction.

All reports of intentional misuse and abuse of the product are also considered SAE irrespective if a clinical event has occurred.

10.1.3 SAE reporting

To ensure participant safety, every SAE, regardless of causality, occurring after the participant has provided informed consent and until 30 days after the last study visit must be reported to Novartis safety immediately, without undue delay, but under no circumstances later than within 24 hours of obtaining knowledge of the events (Note: If more stringent, local regulations regarding reporting timelines prevail). Detailed instructions regarding the submission process and requirements are to be found in the investigator folder provided to each site. Information about all SAEs occurring before EOS visit is collected and recorded on the eSAE page with paper backup and as paper during the 30 days safety follow-up period after EOS; all applicable sections of the form must be completed in order to provide a clinically thorough report.

SAE reporting time frames are as follows:

1. SAEs occurring after the participant has provided informed consent until the time the participant is deemed a Screen Failure must be reported to Novartis.

2. SAEs occurring between time participant signs ICF until time that participant is determined to be a run-in failure must be reported to Novartis.
3. SAEs occurring between time participant signs ICF until 30 days after EOS must be reported to Novartis.

All follow-up information for the SAE including information on complications, progression of the initial SAE and recurrent episodes must be reported as follow-up to the original episode immediately, without undue delay, but under no circumstances later than within 24 hours of the investigator receiving the follow-up information (Note: If more stringent, local regulations regarding reporting timelines prevail). An SAE occurring at a different time interval or otherwise considered completely unrelated to a previously reported one must be reported separately as a new event.

If the SAE is not previously documented in the Investigator's Brochure or Package Insert (new occurrence) and is thought to be related to the study treatment, a PV & PS Department associate may urgently require further information from the investigator for health authority reporting. Novartis may need to issue an IN to inform all investigators involved in any study with the same study treatment that this SAE has been reported.

Suspected Unexpected Serious Adverse Reactions (SUSARs) will be collected and reported to the competent authorities and relevant ethics committees in accordance with EU Guidance 2011/C 172/01, or European Clinical Trial Regulation 536/2014, or as per national regulatory requirements in participating countries.

Any SAEs experienced after the 30 day follow-up period after EOS should only be reported to Novartis Safety if the investigator suspects a causal relationship to study treatment, unless otherwise specified by local law/regulations.

Reporting of SAEs related to AxMP(s)

All SAEs related to any auxiliary medicinal product (whether authorized or not) used in this study must be reported to Novartis within 24 hours of the site becoming aware of it. In assessing causality, the investigators will use the points above. If a suspicion that the medical occurrence could be related to study treatment (or and interaction with study treatment) cannot be ruled out, the reporting rules for study treatment apply.

10.1.4 Pregnancy reporting

Pregnancies

If a trial participant becomes pregnant, the study treatment should be stopped, and the pregnancy consent form should be presented to the trial participant. The participant must be given adequate time to read, review and sign the pregnancy consent form. This consent form is necessary to allow the investigator to collect and report information regarding the pregnancy. To ensure participant safety, each pregnancy occurring after signing the informed consent must be reported to Novartis within 24 hours of learning of its occurrence. The pregnancy should be followed up to determine outcome, including spontaneous or voluntary termination, details of the birth, and the presence or absence of any birth defects, congenital abnormalities, or maternal and/or newborn complications.

Pregnancy should be recorded and reported by the investigator to the Novartis Chief Medical Office and Patient Safety (CMO&PS). Pregnancy follow-up should be recorded on the same form and should include an assessment of the possible relationship to the study treatment and pregnancy outcome. Any SAE experienced during pregnancy must be reported.

After consent is provided, the pregnancy reporting will continue for up to one year after the estimated date of delivery.

10.1.5 Reporting of study treatment errors including misuse/abuse

Study treatment errors are unintentional errors in the prescribing, dispensing, administration of study treatment.

Study treatment misuse refers to situations where the study treatment is intentionally and inappropriately used not in accordance with the protocol.

Study treatment abuse corresponds to the persistent or sporadic, intentional excessive use of a study treatment, which is accompanied by harmful physical or psychological effects.

Study treatment errors and uses outside of what is foreseen in the protocol, including misuse or abuse, must be reported on the AE (or SAE, if the event meets the definition of an SAE) eCRF and reported in the safety database irrespective of it being associated with an AE/SAE within 24 hours of Investigator's awareness.

Table 10-1 **Guidance for capturing the study treatment errors including misuse/abuse**

Treatment error type	Document in Dosing CRF (Yes/No)	Document in AE eCRF	Complete SAE form
Unintentional study treatment error	Yes	Only if associated with an AE	Only if associated with an SAE
Misuse/Abuse	Yes	Yes	Yes, even if not associated with a SAE

For more information on AE and SAE definition and reporting requirements, please see the respective sections.

10.2 Additional Safety Monitoring

Always refer to the local rosuvastatin SmPC.

10.2.1 Liver safety monitoring

Rosuvastatin should be discontinued or the dose reduced if the level of serum transaminases is $> 3x$ ULN (always refer to the local SmPC).

Hepatic Serious Adverse Event(s)

Hepatic SAEs will be specifically collected and assessed throughout the trial to identify the potentially rare cases of drug-induced liver injury (DILI), none of which have been seen so far with inclisiran.

Participants with transaminase increase combined with total bilirubin increase may be indicative of potentially severe DILI and should be considered as clinically important events and assessed appropriately to establish the diagnosis. Hepatic AEs will be assessed as serious under “medically significant” even if other seriousness criteria are not met, using the following criteria:

- ALT or AST ≥ 5 x ULN
- ALP ≥ 2 x ULN in the absence of known bone pathology
- For participants with normal ALT and AST and total bilirubin value at baseline: AST or ALT > 3.0 x ULN combined with total bilirubin > 2.0 x ULN (meeting the criteria for a potential Hy’s Law case)
- For participants with elevated AST or ALT or total bilirubin value at baseline: AST or ALT > 2 x baseline AND > 3 x ULN combined with total bilirubin > 2 x baseline AND > 2.0 x ULN (meeting the criteria for a potential Hy’s Law case)

For potential Hy’s Law cases an expedited reporting is required, and will be handled as a serious unexpected adverse event associated with the use of the study treatment (assessing it as medically significant in the absence of any other seriousness criteria). It must be reported as an SAE to the sponsor promptly (i.e., even before all other possible causes of liver injury have been excluded). Reporting should include all available information especially that needed for evaluating the diagnosis, severity and likelihood that the study treatment caused the reaction. For patient monitoring and to better understand potential etiologies, the investigator must initiate a close follow-up until complete resolution of the problem and completion of all attempts to obtain supplementary data.

As DILI is essentially a diagnosis of exclusion, other causes of abnormal liver tests should be considered, and their role clarified before DILI is assumed as the cause of liver injury. The required clinical information will be collected in specific eCRF forms to obtain the medical diagnosis of the most likely cause of the observed laboratory abnormalities.

The evaluation of these elevated LFTs may include a detailed history, as well as relevant information such as review of ethanol consumption, concomitant medications, herbal remedies, supplement consumption, history of any pre-existing liver conditions or risk factors, laboratory tests, imaging and pathology assessments that would have been performed to elucidate the etiology of these hepatic SAEs.

Following appropriate causality assessments, as outlined above, the causality of the treatment is estimated as “probable” i.e. $>50\%$ likely, if it appears greater than all other possible causes of liver injury combined. The term “treatment-induced” indicates probably caused by the treatment, not by something else, and only such a case can be considered a DILI case.

Only cases confirmed on repeat testing meeting the laboratory criteria defined above, with no other alternative cause for LFT abnormalities identified, should be reported as SAE using the term “potential treatment-induced liver injury.” All events should be followed up with the outcome clearly documented.

Permanent discontinuation from study treatment should be the rule if causality assessment indicates that DILI is probable. Please refer to [Section 9.1.1](#) for more details on discontinuation from study treatment.

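### Protocol 10.2.1 leaves unclear whether repeat testing and exclusion of other causes are conditions for filing a hepatic SAE or only for using one reporting term

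*Protocol*

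**What the plan says.** Three statements in the protocol bear on when a hepatic event becomes a reported SAE.

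- **Section 10.2.1, seriousness.** "Hepatic AEs will be assessed as serious under" the medically significant criterion if they meet any of four laboratory conditions: ALT or AST at least 5 × ULN; ALP at least 2 × ULN without known bone pathology; and two definitions of a potential Hy's Law case, one for normal and one for elevated baseline values. For a potential Hy's Law case, "an expedited reporting is required, and will be handled as a serious unexpected adverse event associated with the use of the study treatment". On timing: "It must be reported as an SAE to the sponsor promptly (i.e., even before all other possible causes of liver injury have been excluded").
- **Section 10.1.3, the general rule.** It covers "every SAE, regardless of causality, occurring after the participant has provided informed consent", with a limit of 24 hours from awareness. Later information goes in as follow-up to the first report.
- **Section 10.2.1, after the description of the work-up.** A restrictive sentence says that only those "confirmed on repeat testing meeting the laboratory criteria defined above, with no other alternative cause for LFT abnormalities identified, should be reported as SAE". It then goes on to name the term for that report, *potential treatment-induced liver injury*.

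**The concern.** The last statement uses the same verb as the Hy's Law text (report as an SAE) and points back to the same laboratory criteria, but adds two conditions. Repeat confirmation is not mentioned in the earlier text. Absence of another cause is what the earlier text says not to wait for in a potential Hy's Law case. The sentence opens with a restrictive word and comes last in the sequence, so a site could treat it as the operative instruction.

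A site that did so would hold back the SAE until the work-up was finished, and these are cases for which the protocol asks for expedited reporting. Hepatic SAE counts would then also depend partly on how each site read one sentence.

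**Working it through.** No arithmetic underlies the main point, so the check is a side-by-side reading. The later sentence can be read in two ways:

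- **Filing rule:** it limits which cases are reported as SAEs at all.
- **Naming rule:** it limits which reported SAEs carry the specific term.

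| Situation | Early 10.2.1 text and 10.1.3 | Later sentence as filing rule | Later sentence as naming rule |
|---|---|---|---|
| First sample meets a Hy's Law definition, not yet repeated | SAE now | Wait | SAE now, term withheld |
| First sample shows ALT at least 5 × ULN, assessed as a hepatic AE | Serious, so SAE within 24 hours | Wait | SAE now, term withheld |
| Repeat confirms, another cause is found | SAE, since causality is irrelevant | No SAE | SAE, without the term |
| Repeat confirms, no other cause found | SAE | SAE | SAE, term applied as follow-up |

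The filing rule conflicts with the other text in the first three rows. The naming rule conflicts in none.

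Three features of 10.2.1 favour the naming rule:

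1. The sentence does not stop at reporting as an SAE; it goes on to specify a term.
2. The preceding text describes the work-up as "performed to elucidate the etiology of these hepatic SAEs", so the cases already have SAE status before their cause is known.
3. The paragraph just before explains what treatment-induced means and when a case counts as DILI. A rule on the use of that label follows naturally.

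Three things remain unresolved:

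1. No sentence states that the naming rule is the one intended.
2. If the term is reserved for confirmed, unexplained cases, 10.2.1 does not say what term the prompt first report carries, or that the label is added later.
3. The back-reference covers all four laboratory criteria, but the explicit instruction not to wait covers only potential Hy's Law cases. For the ALT/AST and ALP criteria the reader has only 10.1.3 to rely on.

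**Reach.** The Amendment 3 rationale gives 1776 randomized participants and 1391 who had completed treatment on 2-Sep-2024, the date of this version. 1776 − 1391 = 385, or 385/1776 = 21.7%, is the most who could still have been on treatment.

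**Effect on analysis.** Hepatic SAEs are not a primary or secondary endpoint (Protocol Table 2-1). SAP 2.7.3 and Table 5-1 tabulate notable liver values, including ALT or AST with bilirubin, from laboratory data, so those tables do not depend on SAE filing. The SAE summaries in SAP 2.7.1 do.

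**The case against.** A reader might infer that the protocol forbids SAE reports for unconfirmed or explained cases, so that no investigator could obey both parts of 10.2.1. The documents do not support that. The sentence is tied to a named term, and its context treats the cases as SAEs already. A site can comply with everything by filing within 24 hours and then updating the report, which 10.1.3 provides for. The duties in 10.1.3 and in the Hy's Law text are also worded as obligations, and a weaker instruction about a term does not clearly override them. All of this stands, and it reduces the problem from a contradiction to an ambiguity.

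A second objection is that a remedy could go too far. The criteria in 10.2.1 apply to hepatic AEs, not to every laboratory value. Section 10.1.1 makes an abnormal value an AE only if it causes signs or symptoms, is clinically significant or needs therapy. The ALP criterion already sets aside known bone pathology. This also stands, and any rewording must respect it.

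The objection does not remove the need for a clarification. The naming rule has to be inferred, in a passage whose purpose is to secure prompt reporting.

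**Conclusion.** Section 10.2.1 is ambiguous on hepatic SAE reporting. The later sentence probably governs only the term, but the protocol does not say so, and a site could reasonably wait for the work-up and delay an expedited report. It is a wording defect worth correcting, with limited impact.

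- **Frequency.** Few cases are expected: the protocol describes DILI as potentially rare and not so far seen with inclisiran. It gives no expected rate for the four criteria under rosuvastatin, so no count can be offered.
- **Delay.** The documents give no turnaround for repeat testing or work-up. A quick repeat might fit within 24 hours; a work-up that includes imaging or pathology is assumed not to.
- **Reach.** The figure of 385 is an upper bound for those still on treatment, since some may have stopped early. SAE reporting runs to 30 days after the last study visit, so some recent completers were also still covered; their number is not given.
- **Analysis.** The primary analysis, power, type I error and laboratory-based liver tables are unaffected. Only the SAE summaries could shift, and by few events.

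**What to change.** Reconcile 10.2.1 with itself and with 10.1.3:

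1. State that hepatic AEs meeting the 10.2.1 criteria, with the ALP bone-pathology exception kept, are reported under 10.1.3 without waiting for repeat testing or exclusion of other causes.
2. State that the later sentence governs only when the term *potential treatment-induced liver injury* may be applied, as follow-up to the initial report.
3. Send sites a short notice.

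This keeps the AE definition in 10.1.1 and creates no duty to report isolated laboratory values.

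As a useful addition, compare central laboratory values with filed hepatic SAEs before database lock, using the 10.2.1 thresholds, and query unmatched cases. This would also pick up any case withheld among participants who had already finished.

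The cost is a sentence or two, one notification and one data check. The downside is a few initial SAE reports that are later reclassified.
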